3.4.3 Binary outcomes

Binary outcomes will be analyzed using a logistic regression model including health system, prior MOUD exposure, and treatment assignment as predictors. The logistic regression model is given by:

$$\log\left(\frac{\Pr(y_{ij} = 1)}{1 - \Pr(y_{ij} = 1)}\right) = \alpha_j + \nu P_{ij} + \beta T_{ij}$$

where α_j are health system-level fixed effects and e^β is the odds ratio for CC-COD/CC-COD+ versus EUC. The statistical hypotheses from the logistic regressions will be of the form:

$$\begin{aligned} H_0: \beta &= 0 \text{ vs} \\ H_1: \beta &\neq 0. \end{aligned}$$

The estimated effects from these models will be converted to risk differences using the recycled prediction approach to estimate marginal effects.⁴ Both odds ratios and risk differences may be reported to improve interpretation.

If necessary, outcomes that require elements from the 6-month follow-up survey may be weighted to account for nonresponse as previously described. Additionally, if we do not have sufficient sample size to support modeling P_{ij} (prior MOUD treatment), then it will be removed from a given model. We will assess this by examining a cross-frequency of P_{ij} with out outcome y_{ij} and ensure that we have at least 20 individuals per cell.

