Opioid use frequency	All study participants	Days of opioid use in the past 30 days from NSDUH	Total days of opioids use (0-30)	Survey
Opioid overdose events	All study participants	Opioid overdose events in the previous three months	Binary, at least 1 event	Survey
Overall Health				
Physical health functioning	All study participants	Veterans RAND 12-item Health Survey (VR-12) – physical health subscale	MEPS ¹ standard	Survey
Mental health functioning	All study participants	Veterans RAND 12-item Health Survey (VR-12) – mental health subscale	MEPS standard	Survey

^b Study participants means all study participants who consented and were randomized to the intervention or to EUC.

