3.4 Statistical models

3.4.1 Notation

Table 8 provides notation used to describe the statistical models. We note that the sample size per primary care clinic where not large enough to support the use of fixed effects by clinics in our regression models. Instead, we utilize fixed effects for health systems. When the sample sizes for the smallest health systems prove too small (e.g., less than 30 for continuous

outcomes), we will collapse the smallest health systems together for the purposes of our regression models.

Table 8: Notation used to describe the statistical models.

Notation	Description
X_{ij}	The baseline characteristics of participant i at health system j , including both demographics and other baseline characteristics.
P_{ij}	An indicator of prior MOUD treatment for participant i at health system j .
T_{ij}	The random treatment assignment of participant i at health system j .
y_{ij}	An outcome measure for participant i at health system j .
R_{ij}	An indicator denoting whether participant i at health system j responded to the 6-month follow-up survey.
M_{ij}	A mediator of the outcome-treatment relationship for participant i at health system j .

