3.4.2 Overview and General Principles

The primary analyses will be performed for the intention-to-treat population, which consists of all randomized subjects. All individual statistical hypotheses will be tested using two-sided tests, with adjustment for multiple testing using a Bonferroni or Benjamini-Hochberg correction. Primary outcomes will be analyzed at a Type I error rate of 1.25% to control the family-wise error rate at 5% (e.g., so $0.05/4=0.0125$ when using a Bonferroni correction or the first p-value threshold for significance with Benjamini-Hochberg). Similarly, secondary and exploratory outcomes will be analyzed at Type I error rates to control family-wise error rate at 5% within domain. See Table 2 and 3 for definition of secondary outcome domains and our exploratory outcomes.

Outcomes derived from the follow-up surveys are subject to nonresponse, and statistical hypotheses based on these outcomes will be tested using nonresponse weighted models, if necessary. Traditionally, a logistic regression model can be specified predicting response using the demographic characteristics listed in Table , the baseline characteristics listed in Table , and the randomized treatment assignment. The model is given by:

$$\log \left(\frac{\Pr(R_{ij}=1)}{1-\Pr(R_{ij}=1)} \right) = \eta_j + \mathbf{X}_{ij} \boldsymbol{\theta} + \gamma T_{ij} + \rho P_{ij}$$

where η_j represent health system fixed effects. The nonresponse weight for participant i in health system j is given by $w_{ij} = \frac{1}{p_{ij}}$, where $p_{ij} = \Pr(R_{ij} = 1)$. However, we will utilize a nonparametric machine learner to estimate our nonresponse weights to allow for more complex relationships between the predictors variables and the odds of being a responder, thereby producing more high-quality nonresponse weights if they are deemed necessary.

To assess whether there is a need for use of nonresponse weights in our final analyses, we will assess how representative our sample of responders is for each outcome using effect sizes (ES) differences. If most of the ES differences are small (e.g., less than 0.1 or 0.2), we will feel good about the representativeness of our sample of responders to the original baseline sample and not utilize nonresponse weights in our final analyses.

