3.5.2 Secondary outcomes

Secondary endpoints are grouped into domains of conceptually related endpoints, and the outcomes will be analyzed adjusting for multiple comparison within domain using a Bonferroni correction. Table 8 provides the grouping of the secondary outcomes into domains, along with the observed outcome distributions, the minimum detectable effect size at 80% power and a family-wise error rate of 5%, and a reference effect size (if available). The vast majority of secondary outcomes are sufficiently powered to detect clinically meaningful effects or effects found in similar interventions.

Table 9: Minimum detectable effect size for secondary outcomes

Outcome	Observed distributions	Minimum detectable effect size	Reference effect size
Mental Health			
Access to MDD and/or PTSD treatment	
 • N=259 • 65.5% access treatment 	19.2 percentage points	None
Quality of care for MDD	
 • N=210 • 8.8% with quality care 	18.9 percentage point	16 percentage points for medication adherence ¹² at 3 months
Quality of care for PTSD	
 • N=300 • 9% with quality care 	15.3 percentage point	Expect similar to MDD
MDD remission	
 • N=405 • 16.0% remission 	15.0 percentage points	15 percentage points ¹³
MDD response	
 • N=405 • 26.2% response 	15.8 percentage points	20 percentage points from CALM ¹³ or 23 percentage points from STEPS-UP ¹¹
PTSD remission	
 • N=368 • 56.2% remission 	17.8 percentage points	Similar to MDD remission
PTSD response	
 • N=365 • 21.6% response 	17.7 percentage points	18 percentage points ¹¹

Active suicidal ideation	
• N=523• 24.2% at 6-months	14.5 percentage point	Any reduction
--------------------------	---	-----------------------	---------------

Substance Use

Opioid use frequency	
• N=523• Mean (sd) = 4.3 (9.6)	0.27 standard deviations; 2.6 raw scale	None
----------------------	---	---	------

Opioid overdose events	
• N=525• 2.1% at 6-months	5.9 pct point reduction	None
------------------------	--	-------------------------	------

Overall Health

Physical health functioning	
• N=525• Mean (sd) = 36.8 (12.0)	3.2 points	Similar to mental health functioning

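### Opioid overdose, with 11 events in 525 people, is assigned an ordinary logistic model with no named test; a default Wald test would be very conservative and the odds ratio not estimable if one arm has no events

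*SAP*

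**What the plan says.** SAP Table 2 defines opioid overdose events over the previous three months on the scale "Binary, at least 1 event", in the Substance Use domain with opioid use frequency. SAP 3.4.3 gives one model for all such outcomes: "Binary outcomes will be analyzed using a logistic regression model including health system, prior MOUD exposure, and treatment assignment as predictors". The hypothesis is that the treatment coefficient is zero. Odds ratios may be reported together with marginal risk differences from recycled predictions. No test statistic is named beyond SAP 3.4.2: "All individual statistical hypotheses will be tested using two-sided tests".

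SAP 3.5.2 plans analysis "adjusting for multiple comparison within domain using a Bonferroni correction". Table 9 in that section shows N=525, "2.1% at 6-months" and a minimum detectable effect of "5.9 pct point reduction" for overdose.

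Two small-sample rules exist. SAP 3.4.3 drops prior MOUD exposure when a cell of its cross-table with the outcome holds fewer than 20 people. SAP 3.4.1 allows small health systems to be merged: "When the sample sizes for the smallest health systems prove too small (e.g., less than 30 for continuous" outcomes). Neither rule counts events or concerns an empty treatment arm, and no exact or penalised method is named.

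**The concern.** Maximum-likelihood logistic regression relies on large-sample approximations that depend on the number of events, not on the number of people. With 11 events in total, the Wald statistic is unreliable when the arms differ sharply, because the standard error grows faster than the coefficient. If one arm has no events, the coefficient has no finite estimate.

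The weakness therefore appears where the intervention effect is largest. Overdose is also one of the two harms that the competitive revision set out to reduce (Protocol 1.1 and 2.1). Two analysts following the same SAP on the same data could report opposite conclusions, depending only on which test their software prints.

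**Working it through.** **Inputs.** N=525 and 2.1% (SAP Table 9); two outcomes in the domain (SAP Table 2), so alpha = 0.05/2 = 0.025, two-sided; 1:1 allocation (SAP 2.7). The split of the 525 by arm and by health system is not given. I assume 262 CC-COD/CC-COD+ and 263 EUC; shares of 48% to 52% and one to five systems of assumed sizes were also tried.

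**Events.** 0.021 × 525 = 11.0. Eleven is the only whole number that rounds to 2.1% (10/525 = 1.9%, 12/525 = 2.3%).

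**The plan's own figure.** A pooled two-proportion test with 262.5 per arm, 2.1% against 8.0%, has mean rate 5.05%. The null SE is √(2 × 0.0505 × 0.9495/262.5) = 0.0191 and the alternative SE is √((0.021 × 0.979 + 0.080 × 0.920)/262.5) = 0.0189. Then (0.059 − 2.241 × 0.0191)/0.0189 = 0.85, giving about 80% power. So 5.9 points reproduces, but as a rise from 2.1%. With 11 events in all, the largest possible difference is 11/263 = 4.2 points.

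**The drop rule.** The two event cells together hold 11 people, so neither can reach 20. Prior MOUD is always dropped for overdose; treatment stays.

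**0 versus 11, without system terms.**
- Wald: the coefficient diverges (about −18, SE about 2,900 when iteration stops), so p > 0.99.
- Likelihood ratio: the log-likelihood is −45.68 with treatment and −53.40 without; 2 × 7.72 = 15.4, p = 0.00009.
- Firth: in a 2×2 table this adds 0.5 to each cell, so OR = (0.5 × 252.5)/(262.5 × 11.5) = 0.04; penalised-likelihood p = 0.0004.
- Fisher's exact: p = 0.0009.
- Risk difference: −11/263 = −4.2 points; SE = √(0.0418 × 0.9582/263) = 0.0123; 95% interval −6.6 to −1.8. It excludes zero beside a Wald p near 1.

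**1 versus 10.** The log OR is ln[(1 × 253)/(261 × 10)] = −2.33; SE = √(1 + 1/261 + 1/10 + 1/253) = 1.05; z = −2.22; Wald p = 0.027.

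| Events, CC-COD/CC-COD+ : EUC | Wald p | Likelihood-ratio p | Firth p | Fisher p |
|---|---|---|---|---|
| 0 : 11 | >0.99 | 0.00009 | 0.0004 | 0.0009 |
| 1 : 10 | 0.027 | 0.003 | 0.005 | 0.011 |
| 2 : 9 | 0.052 | 0.027 | 0.035 | 0.063 |

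Across the system mixes and arm splits tried, the Wald p at 0 : 11 never fell below 0.99, and at 1 : 10 it ran from 0.020 to 0.032, on both sides of 0.025. At 4 : 7 the Wald and likelihood-ratio tests agree (0.37 and 0.36).

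**Simulated rejection at 0.025**, N=525, with health-system terms; ranges cover separate runs and assumed system mixes.

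| True rates, EUC vs CC-COD/CC-COD+ | Wald | Likelihood ratio | Firth | Fisher |
|---|---|---|---|---|
| 2.1% vs 2.1% | 0 to 0.6% | 2.0 to 3.6% | 1.4 to 2.5% | about 1.5% |
| 3.95% vs 0.25% | 20 to 26% | about 89% | about 84% | about 76% |
| 3.5% vs 0.5% | about 19% | about 70% | 61 to 64% | about 52% |
| 2.8% vs 1.4% | about 4% | – | 11 to 12% | – |

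**How likely is an empty arm?** Given 11 events in equal arms, the chance that all fall in EUC is about (1/(1+OR))^11: 0.05% at OR 1, 1.2% at OR 0.5, 13% at OR 0.2 and 35% at OR 0.1.

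**The case against.** The strongest reply is that the SAP never prescribes a Wald test. A likelihood-ratio test of exactly the stated model gives p < 0.001 at 0 versus 11 and good power, though it is somewhat liberal (up to 3.6% at nominal 2.5%). The marginal risk difference in section 3.4.3 also survives. Both points stand. A reader might infer that the plan, as written, would report a complete elimination of overdoses as non-significant. The documents do not support that: it depends on an unstated choice of test, and the risk difference would still show the effect.

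A reader might also blame the health-system fixed effects. That does not hold either. A system with no events sends only its own intercept to infinity and carries no information on treatment; the Wald p at 0 versus 11 is the same with no system terms at all. Section 3.4.1 also provides for merging small systems, even though its only stated cut-off is for continuous outcomes.

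Third, the benefit is confined to large effects. At an odds ratio near 0.5 no method has useful power, and for balanced splits the choice hardly matters. Only 68 of 797 participants followed the competitive-revision protocol (SAP 2.6), so the pooled arm mostly received the version without overdose content. This limits the importance of the point.

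What remains is that the test is unspecified for an outcome whose event count was already known, that the default test has far below its nominal error rate, and that the odds ratio and its interval fail under any unpenalised test when an arm is empty.

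**Conclusion.** The point holds as a specification gap with a cheap remedy. With 11 events, a default Wald test rejects about 0 to 0.6% of the time under no effect, and has about 20 to 26% power where Firth has about 84% (3.95% vs 0.25%). The difference is not limited to an empty arm: at 1 versus 10, Wald gives about 0.027 and Firth about 0.005 against a threshold of 0.025. With an empty arm the odds ratio is not estimable, and a p-value near 1 could stand beside a risk difference of −4.2 points whose interval excludes zero.

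This rests on a near-equal arm split, assumed health-system sizes, and use of the Wald test for the power and type I error contrasts. It does not show that the planned analysis will fail, since an empty arm needs a large true effect. It does not implicate the health-system terms.

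**What to change.** In SAP 3.4.3, before unblinding, state that opioid overdose events, and any binary outcome with very few events or an empty arm-by-outcome cell, are analysed with Firth-penalised logistic regression. The test and interval should come from the profile penalised likelihood, with Fisher's exact test as an unadjusted check. Define very few as a number of events, chosen from counts pooled over arms. If the blind has already been broken, report this analysis as added afterwards.

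The cost is a short addition to the SAP and a standard package; endpoint, population and alpha do not change. There are two downsides. The odds ratio is shrunk slightly towards 1. Firth predictions are also pulled slightly towards 0.5: at 0 versus 11 they are 0.5/263 = 0.19% and 11.5/264 = 4.36%, against observed 0% and 4.18%. The marginal risk difference therefore needs an intercept correction, or the unadjusted risk difference should be reported instead.

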2.6 Study design

This study is a stratified randomized trial testing CC-COD versus EUC, with strata defined by prior MOUD exposure and primary care clinic.

As part of the CR, we initially planned to compare CC-COD+ to CC-COD, with MOUD continuity of care as the primary outcome. However, despite sustained and targeted efforts, recruitment was lower than expected, and we did not reach our targeted enrollment goals for either CC-COD or CC-COD+. Based on input from our research advisory board and NIH project officer, we now plan to combine the CC-COD and CC-COD+ samples when analyzing the data for additional information about the potential effectiveness of the intervention. Since the Collaborative Care Model is identical across both trials, and the only difference between the arms is in the additional clinical modules supported by CC-COD+, combining the active CC-COD and CC-COD+ arms for an exploratory analysis should provide additional precision around the estimated treatment effect for CC-COD/CC-COD+.

The study's original target sample size was 900, with an additional 300 patients targeted for the CR, for a combined target of 1200. Our final sample size was 797 (729 following the original protocol and 68 following the protocol from the CR). This analysis plan has been modified to include actual final power calculations calculated prior to breaking the blind but after all data collection ended.

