2.7 Randomization

After a baseline assessment, study participants will be randomized 1:1 into CC-COD/CC-COD+ or EUC. A stratified randomization design will be used, with the strata determined by primary care clinic and prior MOUD exposure. A randomization list will be generated for each stratum and include randomly permuted block sizes of 2 and 4. We will stratify on prior MOUD to mitigate confounding, as patients who have used MOUD previously are more likely to initiate MOUD subsequently. Research staff will access the randomization module in REDCap. Staff will enter which prior MOUD exposure stratum and clinic the patient is in, and the intervention arm assignment will be generated.

We extended the randomized trial from the original study to implement CC-COD+. All participating clinics started the study with enrolled patients being randomized between CC-COD and EUC. Three health systems then transitioned to randomizing patients between CC-COD+ and EUC. The remaining health system did not transition to CC-COD+ because they did not enroll sufficient patients to justify transitioning to CC-COD+. Table 5 provides a timeline of when health systems transitioned to CC-COD+.

Table 5: Competitive Revision Recruitment Timeline

Site Groups	Date of CC-COD+ Transition
Health System 1 (includes 7 clinics)	08/29/2022
Health System 3 (includes 3 clinics)	07/13/2023
Health System 4 (includes 3 clinics)	08/28/2023

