3.4.4 Continuous outcomes

Continuous outcomes will be analyzed using a linear regression model including health system, prior MOUD exposure, and treatment assignment as predictors. The linear regression model is given by:

$$y_{ij} = \alpha_j + \nu P_{ij} + \beta T_{ij} + e_{ij}$$

where α_j are clinic-level fixed effects, β is the effect of CC-COD over EUC, and e_{ij} is an independent and identically distributed mean zero error term. The statistical hypotheses from the linear regressions will be of the form:

$$H_0: \beta = 0 \text{ vs}$$

$$H_1: \beta \neq 0.$$

If necessary, outcomes that require elements from the 6-month follow-up survey may be weighted to account for nonresponse as previously described. Again, if we do not have sufficient sample size to support modeling P_{ij} (prior MOUD treatment), then it will be removed from a given model. We will assess this for each continuous outcome by examining if we have at least 30 individuals with and without prior MOUD treatment in our analytic sample.

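### The SAP drops prior MOUD, a randomisation stratum, from models under two sample-size rules; on its own figures this is unavoidable for three binary secondary endpoints and only conditionally possible for primary buprenorphine access

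*SAP*

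**What the plan says.** SAP 2.6 describes a trial randomised "with strata defined by prior MOUD exposure and primary care clinic", and 2.7 gives the reason for the first factor: "patients who have used MOUD previously are more likely to initiate MOUD subsequently". Sections 3.4.3 to 3.4.5 name prior MOUD, health system and treatment as the predictors in every outcome model. Clinic, the other stratification factor, is already represented only by health system (3.4.1).

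Two rules then allow prior MOUD to be taken out.

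- **Binary outcomes (3.4.3).** If the sample cannot support the term, "then it will be removed from a given model". The check is a table of prior MOUD against the outcome, to "ensure that we have at least 20 individuals per cell". The table is not split by arm.
- **Continuous outcomes (3.4.4) and the Cox model for buprenorphine access (3.4.5).** The check is "examining if we have at least 30 individuals with and without prior MOUD treatment in our analytic sample". Outcome values play no part. Section 3.4.5 repeats this sentence and still speaks of continuous outcomes, although it governs a time-to-event primary.

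The note to SAP Table 11 states, without exception, that the primary effect estimates come from models containing clinic, prior MOUD and treatment.

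**The concern.** A variable used to stratify randomisation would normally stay in the analysis model, because the design has already balanced it and adjustment recovers the precision which that balance buys. Prior MOUD is a single parameter, chosen because it was expected to be prognostic. Under the binary rule, the pooled outcome frequency decides whether it stays. Endpoints in the same multiplicity family would then be adjusted differently, and some odds ratios would be conditional on prior MOUD while others would not.

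The rule also does little about the problem it is meant to solve. It removes one parameter, keeps the health-system terms, and leaves a model with about 11 overdose events to ordinary maximum likelihood.

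**Working it through.** **Inputs.** N and observed rates are from SAP Table 9, primary analysis sizes from SAP 3.5.1, the 20 and 30 thresholds from SAP 3.4.3 to 3.4.5, 1:1 allocation from SAP 2.7, and two-sided tests from SAP 3.4.2. No prior-MOUD split is given for any analysis set.

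**Are the Table 9 rates the SAP's working inputs?** I used the two-proportion formula, with n per arm, p0 the observed rate, p1 = p0 + effect and m their mean:

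power = Φ{[effect·√n − z·√(2m(1−m))] / √(p0(1−p0) + p1(1−p1))}

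Alpha is 0.05/8 = 0.00625 for the Mental Health domain and 0.05/2 = 0.025 for Substance Use. At the stated minimum detectable effects the power is:

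- Quality of care for MDD, N=210, 8.8%, 18.9 points: 0.799
- Quality of care for PTSD, N=300, 9%, 15.3 points: 0.800
- Opioid overdose, N=525, 2.1%, 5.9 points: 0.803

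All three agree with the stated 80%, so the sizes and rates can be relied on.

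**Binary rule.** Two event cells of at least 20 need at least 40 events, however prior MOUD is distributed.

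| Endpoint | Events = N × rate | Rate needed for 40 events |
|---|---|---|
| Quality of care for MDD | 210 × 0.088 = 18.5 | 40/210 = 19.0% |
| Quality of care for PTSD | 300 × 0.09 = 27.0 | 40/300 = 13.3% |
| Opioid overdose | 525 × 0.021 = 11.0 | 40/525 = 7.6% |

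All three fail under any split. (8.8% of 210 is not a whole number of people; 18 or 19 makes no difference.) The other six binary secondary endpoints have roughly 65 to 207 events and 89 to 396 non-events, so they depend on the split. The closest is MDD remission: 405 × 0.16 = 64.8 events, which fails if the smaller prior-MOUD group holds fewer than 20/64.8 = 31% of them.

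**Does removal relieve sparsity?** Assume four health systems, as in SAP Table 6. The slopes are then 3 + 1 + 1 = 5 with prior MOUD and 4 without. Events per parameter move from 18.5/5 = 3.7 to 4.6 (MDD), 27/5 = 5.4 to 6.8 (PTSD) and 11/5 = 2.2 to 2.8 (overdose). The models remain sparse.

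**Thirty-per-group rule.** For buprenorphine access, 30/137 = 21.9%, so prior MOUD is lost if its prevalence is below about 22% or above about 78%. For the other primaries at the SAP 3.5.1 sizes, the smaller group would have to be under 30/392 = 7.7%, 30/405 = 7.4% or 30/368 = 8.2%.

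**Size of the harm, by simulation with assumed effects.**

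- *Type I error* (N=300, half with prior MOUD, prior-MOUD odds ratio 1 to 5, nominal 0.05): 0.041 to 0.046 without the stratum, 0.043 to 0.050 with it.
- *Attenuation* (same set-up, true log odds ratio 1.2, prior-MOUD odds ratio 5): the median estimate is 1.12 without the stratum and 1.23 with it.
- *Power* (SAP sizes, alphas and detectable effects, observed rate as control rate, half with prior MOUD, no health-system term), without versus with prior MOUD: quality of care for MDD 0.79/0.80, 0.80/0.82 and 0.79/0.83 at prior-MOUD odds ratios 2, 3 and 5; quality of care for PTSD 0.81/0.82, 0.79/0.81 and 0.81/0.84; overdose 0.82/0.82 at odds ratios 2 and 3.

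**The case against.** The rules are written down in advance, the binary table pools the arms, and SAP 2.2 says the plan was finalised before unblinding. Nothing selects on the treatment effect. The simulated power loss is 0 to 4 points, and the upper end assumes a prior-MOUD odds ratio of 5. The documents claim only that prior MOUD predicts later MOUD initiation, not overdose or the quality of depression or PTSD care. Section 3.4.3 also converts effects to marginal risk differences, whose meaning does not change with the covariates, so attenuation concerns the odds ratio. The 30-per-group rule ignores the outcome and is a conventional safeguard. All of this stands, and it limits the size of the point.

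It does not justify the rules. Removing the term gives almost no relief from sparsity, and the tests in 3.4.3 are on the log odds ratio.

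Three stronger readings are tempting, and the documents do not support them:

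- **An outcome-dependent cell count threatens a primary endpoint.** The 20-per-cell rule covers binary outcomes only, and SAP Table 1 has one time-to-event primary and three analysed by linear regression. The exposure of buprenorphine access comes from the outcome-free rule, and whether its threshold is crossed is unknown.
- **The false-positive rate is inflated.** The rule is pre-specified and pooled, and the simulation shows a slightly conservative test.
- **Standard errors become too large in the three affected models.** That describes a linear model. In logistic regression the estimate shrinks and its standard error falls slightly (0.410 without against 0.418 with prior MOUD, for quality of care for MDD at a prior-MOUD odds ratio of 3).

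**Conclusion.** The point holds in a limited form. If the final analysis sets match SAP Table 9, prior MOUD will be dropped from the models for quality of care for MDD, quality of care for PTSD and opioid overdose. For MDD remission and the other five binary secondary endpoints this depends on an unreported split. For primary buprenorphine access, removal is possible but conditional on a prevalence outside about 22% to 78%. For the other three primaries it would need a group below roughly 8%.

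The consequences are modest: 0 to 4 points of power in the simulated cases, attenuated odds or hazard ratios, and unequal adjustment within one Bonferroni family. There is also a plain inconsistency, because the Table 11 note promises prior MOUD in every primary model while 3.4.4 and 3.4.5 allow its removal. The simulated sizes rest on an assumed 50% prior-MOUD share and assumed prognostic strength. The event-count result needs neither assumption.

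**What to change.** Delete both removal rules and keep prior MOUD in every model.

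- **Sparse binary outcomes.** Keep prior MOUD and the health-system terms, collapsed if needed, in a Firth-type penalised logistic model, with the intercept correction that marginal risk differences require for rare events. Alternatively, use a Mantel-Haenszel risk difference stratified by both prior MOUD and health system; stratifying by prior MOUD alone would lose the health-system adjustment.
- **Cox model for buprenorphine access.** Keep prior MOUD as a covariate or stratify the baseline hazard by it. Correct the sentence in 3.4.5 that refers to continuous outcomes.
- **Table 11 note.** Bring it into line with 3.4.1 and 3.4.4 to 3.4.5, including whether the fixed effects are for clinic or health system.

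If the sponsor prefers to keep a removal rule, the minimum is to state before unblinding which models omit prior MOUD, since Table 9 already settles three of them.

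The cost is SAP wording and slightly more analysis work with standard methods. The penalised method must be made compatible with nonresponse weights if those are used. No new data are needed.
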